#### ***Change from Baseline in log10 Viral Load***

The change from baseline in log10 viral load will be assessed at specified time points by a MMRM. Patients who have achieved a level below the limit of detection will be included in the analysis at half the lower limit of detection. For this endpoint, Last Observation Carried Forward (LOCF) will be used to impute values for all patients. The treatment effect for the difference at each time point, and the average slope up to each time point for each treatment group will be presented along with a 95% CI.

#### **Safety Analysis**

Safety variables include incidence of AEs (or TEAEs), laboratory test results, and vital signs. All safety analyses will be based on the Safety Population. No formal statistical analysis of the safety data will be performed.

Adverse events will be coded according to MedDRA, version 23.0 dated 19 Apr 2020 (exclusively meant for COVID-19) or later.

The number and percentage of patients with TEAEs, SAEs, TEAEs related to study treatment, SAEs related to study treatment, TEAEs leading to treatment discontinuation, TEAEs leading to study discontinuation, and TEAEs leading to death will be summarized by SOC, PT, and treatment group. In addition, the severity of TEAEs and relationship to study treatment will be summarized by SOC, PT, and treatment group.

Test values and change from baseline will be summarized descriptively by treatment group for specific laboratory test results and vital signs. Where applicable, shift tabulations will be presented for specific laboratory test results by treatment group. Where applicable, number and frequency of clinically significant abnormal values for specific laboratory test results will be presented.

#### **Pharmacokinetic Analysis**

Pharmacokinetic parameters will be determined using population PK modeling approach. The sparse PK samples will be pooled with PK data from other clinical studies for population PK analysis. PK profiles will be predicted and subsequently PK parameters will be estimated. Correlations between PK and pharmacodynamic (efficacy or safety) may be explored, including the relationship between drug exposure and viral elimination dynamics, if data permit. The methodology for PK analysis will be documented in a PK Analysis and Reporting Plan outside of this protocol.

#### **Interim Analysis**

A single interim analysis will be conducted after 97 resolution events have occurred.

## LIST OF ABBREVIATIONS

Abbreviation	Definition
AE	adverse event
ALP	alkaline phosphatase
ALT	alanine aminotransferase
ANOVA	analysis of variance
AST	aspartate aminotransferase
AUC 0-24	area under the concentration-time curve during 24 hours
CETP	Cholesteryl Ester transfer protein
CFR	Code of Federal Regulations
CHD	coronary heart disease
CI	confidence interval
C max	maximum concentration
COVID-19	Coronavirus Disease of 2019
CRO	Contract Research Organization
CT	computerized tomography
DMC	Data Monitoring Committee
EC	Ethics Committee
ECMO	extracorporeal membrane oxygenation
eCRF	electronic Case Report Form
EOT	End of treatment
ePRO	electronic patient-reported outcome
FDA	Food and Drug Administration
GCP	Good Clinical Practice
HDL-C	high-density lipoprotein cholesterol
HR	hazard ratio
IC 50	half maximal inhibitory concentration
ICF	Informed Consent Form
ICH	International Council for Harmonisation
IRB	Institutional Review Board
ITT	Intention-to-treat
IVRS/IWRS	Interactive Voice/Web Response System
LOCF	Last Observation Carried Forward
MDRD	Modification of Diet in Renal Disease
MedDRA	Medical Dictionary for Regulatory Activities
MMRM	Mixed-Effect Model Repeated Measure
PCR	polymerase chain reaction
PK	pharmacokinetic
PP	Per Protocol
PT	preferred term
QTc	corrected QT
SAE	serious adverse event
SARS-CoV-2	Severe Acute Respiratory Syndrome CoronaVirus 2
SOC	system organ class (MedDRA classification)
TEAE	treatment-emergent adverse event
ULN	upper limit of normal
WHO	World Health Organization

## 1. INTRODUCTION

In 2019, an outbreak of respiratory disease caused by a novel coronavirus was first detected in Wuhan City, Hubei Province, China. The virus has been named Severe Acute Respiratory Syndrome CoronaVirus 2 (SARS-CoV-2), and the disease it causes has been named Coronavirus Disease of 2019 (COVID-19). This virus has now been detected in many locations internationally, and COVID-19 was characterized as a pandemic by the World Health Organization (WHO) on 11 March 2020. As of 22 October 2020, WHO reported approximately 41 million COVID-19 positive cases and included approximately 1,128,000 deaths.

SARS-CoV-2 can cause a potentially fatal disease. COVID-19 can range from mild to severe disease, the latter including pneumonia, severe acute respiratory syndrome, multi-organ failure, and death. FDA provided emergency use authorization to remdesivir for the treatment of hospitalized COVID-19 patients. However, there is a need for treatment, as well as to have a clinically effective antiviral drug for the prevention of COVID-19. Clinical management includes symptomatic and supportive care, such as supplemental oxygen, mechanical ventilation, and extracorporeal membrane oxygenation (ECMO) when indicated. There is an urgent need for safe and effective anti-SARS-CoV-2 drugs.

The main protease (Mpro) of SARS-CoV-2 is a key enzyme that plays a pivotal role in mediating viral replication and transcription. Dalcetrapib and its metabolite dalcetrapib-thiol is known to covalently bind to Cysteine13 of the Cholestryl Ester transfer protein (CETP). It is speculated that it may form a disulfide bond with Cysteine145 of Main Protease (3CLMpro) of SARS-CoV-2 and inactivate the enzyme therefore stopping the viral replication and transcription in cells. In vitro results are provided in Section 1.2.

### 1.1. Study Rationale

This placebo-controlled, Phase 2a proof-of-concept clinical study will evaluate efficacy and safety of dalcetrapib in outpatients patients with mild to moderate, symptomatic, confirmed COVID-19.

Selection of doses in the study is discussed in [Section 3.4](#).

### 1.2. Background

Dalcetrapib is being investigated for coronary heart disease (CHD) (NCT00658515) in CHD patients. Dalcetrapib is a compound selected for its capacity to modulate plasma CETP activity and increase high-density lipoprotein cholesterol (HDL-C) levels. Dalcetrapib has been evaluated in several large clinical trials, most notably dal-OUTCOMES, a 15,871 patient trial designed to evaluate its effect in patients with recent acute coronary syndrome. As compared with placebo, dalcetrapib did not alter the risk of cardiovascular morbidity and mortality or total mortality despite an effect on HDL-C levels (30% increase). However, the trial demonstrated the safety and tolerability of dalcetrapib in this population.

Molecular docking investigations suggested that dalcetrapib-thiol binds to the active site of the SARS-CoV-2 main 3CL protease with a delta G value of -8.5 kcal/mol ([Table 1](#)).

[figure not shown]
**Table 1: Molecular Docking Data of Dal-thiol and Dal-dimer**

	MPro ΔG Kcal/mol	CETP ΔG Kcal/mol
Dal-ester	-8.62	-8.90
Dal-Thiol	-8.72	-8.07
Dal-DIMER	-10.14	-10.66
Natural substrate of Main Protease	-10.99	-

In vitro data from SARS-CoV-2 infected cultured cell line confirmed antiviral activity and no obvious toxicity was observed in the in vivo toxicity study.

Remdesivir, an injectable intravenous treatment for severe forms of COVID-19, is currently the only treatment approved by the FDA. In vitro data for remdesivir and dalcetrapib confirm the inhibition of viral replication in renal monkey cells with pre-incubation to achieve lower half maximal inhibitory concentration (IC50). Dalcetrapib inhibited main 3CL protease activity both in vitro and viral replication in cells with IC50 values of 14.4±3.3 μM and 17.5±3.5 μM. Near-complete inhibition of protease activity persisted despite elution of dalcetrapib approximately 100 times below its IC50, suggesting stable protease-drug interaction.

**Figure 1: Inhibition of Viral Replication in Renal Human Cell**

IC50 = half maximal inhibitory concentration

### **1.3. Risk-benefit Assessment**

Dalcetrapib is an oral, safe and generally well-tolerated drug which could target mild, moderate, and severe forms of the COVID-19, and possibly prevent COVID-19 in high-risk or exposed patients.

No obvious toxicity was observed in the in-vivo toxicity studies. The major dose-limiting finding associated with dalcetrapib in monkeys was gastrointestinal toxicity (diarrhea and loose stools). In general, dalcetrapib has been well-tolerated in patients with CHD. In the short-term (<12 weeks) Phase 1 and 2 studies, the incidence of adverse events (AEs) leading to discontinuation of dalcetrapib (300, 600, and 900 mg) was low across the Phase 1 healthy volunteer and Phase 2 patient studies. The majority of the AEs were of mild or moderate intensity. The most frequently reported AEs were those from body system organ classes of gastrointestinal system and nervous system, and included diarrhea, stool abnormalities, and headache.

More detailed information about the known and expected benefits and risks and reasonably expected adverse events of dalcetrapib may be found in the Investigator's Brochure.

As the study subjects targeted are patients with limited treatment options, the study supports further investigation of dalcetrapib in patients with mild to moderate symptoms due to COVID-19 in a Phase 2a setting.

## 2. OBJECTIVES AND ENDPOINTS

### 2.1. Objectives

The primary efficacy objective of the study is:

- To evaluate the time to sustained clinical resolution of symptoms in patients with confirmed, mild to moderate, symptomatic COVID-19 treated with dalcetrapib.

Sustained clinical resolution is defined as occurring when no key COVID-19 related symptom has a score higher than 1 over a 72-hour period (as documented using an electronic patient-reported outcome [ePRO] instrument), except for sense of smell and taste (items 13 and 14) where the score should be 0 over a 72-hour period. The time to resolution will be taken as the time from randomization until the first day of the last 72-hour period where the patient meets the definition of resolution within 28 days. Patients who do not meet the definition of resolution 28 days after randomization will be considered not resolved.

The secondary efficacy objectives of the study are:

- To evaluate the change from baseline in COVID-19 symptom severity score at all collected time points
- To evaluate time to complete clinical resolution, defined in the same way as the primary endpoint, but considering that all symptoms must resolve to a score of 0 for 72 hours
- To evaluate the time to viral clearance using SARS-CoV-2 polymerase chain reaction (PCR)
- To evaluate change from baseline in log10 viral load
- To evaluate the WHO Clinical Outcome Scale (9-point scale) at Day 3, Day 5, Day 10, and Day 28
- Rate of hospitalization through Day 28
- To evaluate the rate of progression to oxygen therapy through Day 28
- To evaluate the duration of hospitalization
- To evaluate the mortality rate by Day 28

The safety objective of the study is:

- To assess the safety and tolerability of dalcetrapib active doses compared to placebo in patients with COVID-19

The pharmacokinetics (PK) objective of the study is:

- To evaluate the PK of dalcetrapib in patients with COVID-19

## 2.2. Endpoints

The primary efficacy endpoint is:

- Time to sustained clinical resolution.

Sustained clinical resolution is defined as occurring when no key COVID-19 related symptom has a score higher than 1 over a 72-hour period (as documented using an electronic patient-reported outcome [ePRO] instrument), except for sense of smell and taste (items 13 and 14) where the score should be 0 over a 72-hour period. The time to resolution will be taken as the time from randomization until the first day of the last 72-hour period where the patient meets the definition of resolution within 28 days. Patients who do not meet the definition of resolution 28 days after randomization will be considered not resolved.

The secondary efficacy endpoints are:

- Time to complete clinical resolution
- Change from baseline in COVID-19 total symptom score
- Score on the WHO Clinical Outcome Scale (9-point scale)
- Rate of hospitalization
- Rate of progression to oxygen therapy
- Duration of hospitalization
- Time to viral clearance based on PCR test for SARS-CoV-2
- Change from baseline in log10 viral load
- Mortality rate

### 3. INVESTIGATION PLAN

#### 3.1. Overall Study Design and Plan Description

This is a randomized, double-blind, multicenter, Phase 2a proof-of-concept study in outpatients with confirmed, mild to moderate, symptomatic COVID-19. Dalcetrapib inactivates the 3CLMpro enzyme of Corona virus and therefore stops the viral replication and transcription in cells. It is being planned to use for treatment in patients with COVID-19.

Up to 60 sites in the United States and Canada, and other countries as appropriate based on the pandemic situation, are planned to enroll patients.

Total duration of study participation is up to 32 days. The screening period is planned to occur between 48 to 24 hours prior to dosing. Randomization will occur during the Screening/Baseline visit in order for treatment to be dispensed in time for start of first dose on Day 1. Patients will either receive dalcetrapib 900, 1800, or 3600 mg or placebo for 10 days and be followed for 18 days of follow-up. The study design is summarized in [Figure 2](#).

It is anticipated that 208 patients will be randomized in one of the dalcetrapib treatment arms or placebo (52 patients to each of 900 mg, 1800 mg, 3600 mg and placebo) for 10 days. Patients will be randomized and receive first dose of study drug within 72 hours of receiving a positive PCR or Point-of-care test for SARS-CoV-2. Patients need to have at least two of the 14 common COVID-19-related symptoms described in the inclusion criteria rated as mild or moderate, as evaluated by ePRO assessment. Symptoms will be assessed at each study visit daily for the first 10 days, then at Day 14 and Day 28, and as clinically indicated. Symptoms will be evaluated as absent, mild, moderate, or severe depending on their impact on activity of daily living.

[figure not shown]
SARS-CoV-2 viral loads will be obtained by both saliva (Oragene) collection and mid-turbinate nasal swab self-collected under supervision of healthcare professional (virtual or home visit) at Screening/Baseline, Day 1, Day 3, Day 5, Day 7, Day 10, and Day 28. Patients who require hospitalization after initiation of study treatment will be followed for vital status through Day 28.

#### Study Visit Procedures

Study visits (virtual, study site or home visits by a healthcare professional) will take place on Days 1, 3, 5, 7, 10, 14, and 28. Screening/Baseline assessments may all be performed on the same calendar day and may be performed at the study site or as a home visit. For visits which include bloodwork, sample collection may be done by a visiting healthcare professional or at the study site (as long as the patient has no worsening of respiratory symptoms or no fever within 24 hours). Other visits may be conducted remotely using telemedicine.

The samples for viral load testing will be both saliva (Oragene) collection and mid-turbinate nasal swab self-collected under supervision of a healthcare professional. Telemedicine visits such as phone calls or other digital media are to be utilized as much as possible. Study procedures are presented in detail in [Section 7](#).

**Figure 2: Study Design**

D=Day.

### **3.1.1. Data Monitoring Committee**

The study will be overseen by an independent Data Monitoring Committee (DMC). The DMC will review safety data throughout the study. The DMC and Sponsor will review efficacy data at the interim analysis and at the end of the study. A DMC Charter, which includes detailed processes, will be prepared.

One interim analysis will be conducted for efficacy once 97 resolution events have occurred to allow 73 resolution events to have occurred in the two highest dose levels and placebo arm. At the interim analysis, if the average hazard ratio (HR) of the two highest dose levels relative to placebo is greater than 1.45, the study will stop due to efficacy and the program will be able to proceed directly to Phase 3. At the interim analysis, if the HR of the two highest dose levels relative to placebo is between 1.0 and 1.45, the study will continue enrollment until 169 resolution events have occurred. At the interim analysis, if the HR of the two highest dose levels is less than 1.0, the study will be stopped for lack of efficacy.

The members of the committee will include appropriately qualified medical personnel, and other members, as required. Detailed responsibilities of the DMC will be provided in the DMC Charter.

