### **3.2. Discussion of Study Design, Including the Choice of Control Groups**

This study will be double-blind and placebo-controlled to avoid bias in the collection and evaluation of data during its conduct. The Sponsor will remain blinded to the treatment

randomization code until after the database has locked. The Sponsor will perform ongoing review of blinded data. The placebo has been chosen as the control treatment to assess whether any observed effects are treatment-related or simply reflect the study conditions.

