#### **4.5. Stopping Rules**

The study will enroll 208 patients (52 patients to each of 900 mg, 1800 mg, 3600 mg and placebo). One interim analysis will be conducted for efficacy once 97 resolution events have occurred to allow 73 resolution events to have occurred in the two highest dose levels and placebo arm. At the interim analysis, if the average HR of the two highest dose levels relative to placebo is greater than 1.45, the study will stop due to efficacy and the program will be able to proceed directly to Phase 3. At the interim analysis, if the HR of the two highest dose levels relative to placebo is between 1.0 and 1.45, the study will continue enrollment until 169 resolution events have occurred. At the interim analysis, if the HR of the two highest dose levels is less than 1.0, the study will be stopped for lack of efficacy. The DMC will issue a recommendation to enroll patients, or to stop the study depending on interim analysis assessment. The DMC may recommend dropping one or more treatment arms. The DMC will continue to review safety and assess the risk/benefit profile on an ongoing basis.

A DMC Charter, which includes detailed processes, will be prepared.

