### **3 DATASETS ANALYZED**

Subjects who were not eligible for randomization but who have been erroneously randomized into the study will be excluded from all datasets analyzed, if they did not receive study product.

The populations of analysis will be reviewed and confirmed by the sponsor prior to database lock.

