### **6.2.1 Interim Analysis**

The study will be overseen by an independent Data Monitoring Committee (DMC). The DMC will review safety data throughout the study. The DMC will review efficacy data at the interim analysis and at the end of the study. A DMC Charter, which includes detailed processes, will be prepared.

One interim analysis will be conducted for efficacy once 120 patients with a follow-up of 28 days have occurred. No decision to stop the trial will be made based on these efficacy findings as the review of data will occur around the time the last patients enrolled in the study complete the treatment period.

The members of the committee will include appropriately qualified medical personnel, and other members, as required. Detailed responsibilities of the DMC will be provided in the DMC Charter.

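### Protocol 3.1.1 and SAP 2.1 give the sponsor the interim efficacy review, which conflicts with the Protocol 3.2 rule that it stays blinded until database lock

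*Protocol*

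**What the plan says.** Three places put the sponsor in the interim efficacy review, in the same words: the Protocol synopsis (Methodology/study design), Protocol 3.1.1 and SAP 2.1. The sentence is "The DMC and Sponsor will review efficacy data at the interim analysis and at the end of the study".

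Protocol 3.2 points the other way. "The Sponsor will remain blinded to the treatment" "randomization code until after the database has locked" is its rule (one sentence, broken across a page). On what the sponsor looks at during the trial it adds "The Sponsor will perform ongoing review of blinded data".

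Two further places mention the DMC and not the sponsor. SAP 6.2.1 has "The DMC will review efficacy data at the interim analysis and at the end of the study", and the Committees Structure part of Protocol Appendix 3 likewise assigns efficacy review to the DMC.

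On the use of the interim, Protocol 4.5 says "The DMC will issue a recommendation to enroll patients, or to stop the study depending on interim analysis assessment", while SAP 6.2.1 says "No decision to stop the trial will be made based on these efficacy findings". On the analysis sets, SAP 3 says "The populations of analysis will be reviewed and confirmed by the sponsor prior to database lock".

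**The concern.** Taken as written, Protocol 3.1.1 and SAP 2.1 let the sponsor see interim efficacy results that Protocol 3.2 is meant to keep from it. Blinding of the sponsor protects whatever it still decides between the interim and lock. Here that is the confirmation of the analysis populations and any late change to the SAP. If the sponsor has seen results by treatment group first, an outside reader can no longer be assured that those decisions were made without regard to the result, even if they were. The trial's double-blind status would also be open to question on the wording alone.

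**Working it through.** **1. Who sees interim efficacy data**

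- Protocol synopsis, Protocol 3.1.1, SAP 2.1: DMC and sponsor.
- Protocol 3.2: sponsor blinded to the code until after lock; its review in the meantime is described as blinded.
- SAP 6.2.1, Protocol Appendix 3: DMC named, sponsor not named.

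**2. Does precedence settle it?** SAP 1 puts the SAP above the protocol where they differ. But SAP 2.1 names the sponsor and SAP 6.2.1 does not. SAP 2.1 is not simply text carried over untouched: the same paragraph already has the SAP's new trigger of 120 patients with 28 days of follow-up, in place of the protocol's 97 events. So the rule gives no answer.

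**3. Does the interim need results by treatment group?** Under the protocol, yes. Protocol 3.1.1, 4.5 and 8.1 compare the hazard ratio (HR) of the two highest doses to placebo with 1.0 and 1.45. The design behind those limits can be reproduced.

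- Inputs (Protocol 8.1): 73 interim and 127 final events, HR 1.4, alpha 0.2 taken as one-sided, power-family boundary with ρ = 2, futility at HR 1. Allocation is 2:1, because two of the equally sized arms are pooled against placebo.
- Information fraction: 73/127 = 0.575.
- Interim alpha: 0.2 × 0.575² = 0.0661, so z = 1.506.
- HR limit: exp(1.506 / √(73 × 1/3 × 2/3)) = exp(1.506/4.028) = 1.453 (plan: 1.45).
- Final one-sided alpha: 0.1862 (plan: 0.186).
- Power at HR 1.4 with the futility stop: 44.0% at the interim + 36.0% at the end = 80.0% (plan: 80%).

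The interim quantity is therefore a between-arm HR, which pooled data cannot give. SAP 6.2.1 describes its interim as one for efficacy but states no HR threshold.

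**4. How much would someone shown it know?**

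- At the protocol's interim, the interim and final statistics correlate at √0.575 = 0.76.
- At the SAP's trigger, 120/208 = 57.7% of patients have 28 days of follow-up. If the planned 80% resolve in every arm, the three arms of the main comparison supply 120 × 0.75 × 0.8 = 72 events, about the same as 73.

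**5. What is still open to judgement before lock?**

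- ITT (SAP 3.1): a randomization number, a confirmed first dose and no screen-failure report. These are recorded facts, with little room for choice.
- Per-protocol (SAP 3.2): no important deviations, plus a fixed rule of at least 5 days on study medication. Beyond that rule, what counts as important is a judgement. SAP 6.4 and 6.4.4 use this set for sensitivity analysis only.
- SAP changes: Protocol 8.3 requires the SAP to be final before unblinding. Sponsor access at the interim would be an unblinding in substance, so any later change would be hard to defend.

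**6. Does any decision rule need the sponsor to see the data?** No. Under Protocol 4.5 the DMC issues the recommendation. Under SAP 6.2.1 the interim leads to no stopping decision.

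**The case against.** The best defence is that the sponsor's name in SAP 2.1 is leftover wording. SAP 6.2.1 is the operative interim section, and its sentence is the protocol's with the sponsor removed. Detailed processes are left to the DMC charter, which may limit the sponsor to pooled or firewalled output. This stands in part: it is why an actual breach of the blind cannot be asserted. It does not remove the conflict, since a charter would still have to contradict either Protocol 3.1.1 and SAP 2.1 or Protocol 3.2.

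Four stronger readings are tempting and are not supported.

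- *Sponsor access brings no benefit.* This is a Phase 2a trial meant to decide on Phase 3 and its dose, so early efficacy information has planning value. The argument would also combine the SAP's no-stopping rule with the protocol's HR threshold, which belong to different interim plans. What can be said is that neither plan's decision rule needs sponsor access.
- *58% of patients would be visible by arm before the sets are fixed.* The ratio 120/208 is right. But no text says what output the sponsor receives, SAP 3 places the confirmation only before lock and not after the interim, and 28 days of follow-up does not guarantee complete assessments.
- *The primary analysis set is exposed.* ITT membership rests on recorded facts.
- *The SAP was, or could freely be, changed after access.* Amendment 1 is dated 01-JUN-2021, but no interim date is given. Protocol 8.3 forbids a SAP still open at unblinding, and SAP 1 requires deviations to be reported.

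Effects on trial conduct are also limited. SAP 6.2.1 places the review around the time the last patients finish treatment, symptoms are mainly patient-reported, and viral load is measured centrally.

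**Conclusion.** The plan contradicts itself on whether the sponsor sees interim efficacy results before database lock, and it should be corrected. If Protocol 3.1.1 and SAP 2.1 were followed as written with by-arm output, the sponsor would hold results that correlate at about 0.76 with the final test while important deviations for the per-protocol set could still be under review. The 0.76 rests on the protocol's event counts; the match with the SAP trigger assumes 80% resolution in each arm.

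The size of any resulting bias cannot be calculated, because the documents state neither the sponsor's output nor the order of the interim and the population decisions. It is probably modest: the main room for choice is in a sensitivity analysis, and the primary set is largely determined by recorded facts. The case for change is that the wording undoes the plan's own blinding rule and that putting it right is cheap.

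**What to change.** - Remove the sponsor from the interim efficacy review in the Protocol synopsis, Protocol 3.1.1 and SAP 2.1, so that they agree with Protocol 3.2, Protocol Appendix 3 and SAP 6.2.1.
- State in the protocol, the SAP and the DMC charter that by-arm interim output goes only to the DMC, through an independent statistician, and that the sponsor receives only the recommendation until database lock.
- Have the population decisions under SAP 3 made and documented by blinded staff.
- If a pooled, blinded sponsor review was all that was meant, say so in those words.

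The cost is wording in three documents and the loss to the sponsor of early efficacy information for Phase 3 planning. Sample size, event counts, alpha and power are unchanged. One limit remains: if the protocol's published thresholds apply, a recommendation to continue itself tells the sponsor that the HR lies between 1.0 and 1.45. That is far coarser than results by arm.
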